## 5.2. Exclusion Criteria

A subject will not be eligible for inclusion in this study if any of the following criteria apply:

### CONCURRENT CONDITIONS/MEDICAL HISTORY (INCLUDES LIVER FUNCTION AND QTc INTERVAL)

1. History of BPH for which they have received test procedures, medical intervention and/or medicine.
2. History of prostate-related LUTS for which they have received test procedures, medical intervention and/or medicine.
3. History of prostatic surgery (including transurethral resection of the prostate [TURP], balloon dilatation, thermotherapy, and/or stent replacement) or other invasive or minimally invasive procedures to treat BPH.
4. Has other conditions that may cause urinary symptoms (e.g., neurogenic bladder, bladder neck contracture, urethral stricture, bladder malignancy, acute or chronic prostatitis, or acute or chronic urinary tract infections, etc.).
5. History or evidence of prostate cancer (e.g., positive biopsy or ultrasound, suspicious DRE and/or rising PSA).

### CONCOMITANT MEDICATIONS

6. Current or prior use of the following:
  - a. 5 $\alpha$ -reductase inhibitors (finasteride or dutasteride),
  - b. anti-cholinergics (e.g. oxybutynin, propantheline, tolterodine, solifenacin, darifenacin, mirabegron) alpha-adrenoreceptor blockers (i.e., indoramin, prazosin, terazosin, tamsulosin, alfuzosin, doxazosin and silodosin), herbal products for urinary symptoms.
  - c. Use of any investigational study drug within 30 days or 5 half-lives of the drug in question, (whichever is longer), preceding the first study visit.
7. Use within previous 30 days at Visit 1 of:
  - a. PDE-5 inhibitors for erectile dysfunction
  - b. anabolic steroids

## 5.3. Screening/Baseline/Run-in Failures

Screen failures are defined as subjects who consent to participate in the clinical trial but do not meet eligibility criteria and are not subsequently enrolled. In order to ensure transparent reporting of screen failure subjects, to meet the Consolidated Standards of Reporting Trials (CONSORT) publishing requirements, and respond to queries from Regulatory authorities, a minimal set of screen failure information is required including Demography, Screen Failure details, Eligibility Criteria, and Serious Adverse Events (see Section 6.3.1.3). Data for screen failures will be collected in source information at the site and will be transmitted to GSK.

Subjects will be screen failures if they do not meet inclusion/exclusion criteria and do not have a qualifying score on at least one of the two questionnaires (BPE/BPO and/or IPSS screening tools).

#### **5.4. Withdrawal/Stopping Criteria**

The following actions must be taken in relation to a subject who fails to attend the clinic for a required study visit:

- The site must attempt to contact the subject and re-schedule the missed visit as soon as possible.
- The site must counsel the subject on the importance of maintaining the assigned visit schedule and ascertain whether or not the subject wishes to and/or should continue in the study.
- In cases where the subject is deemed ‘lost to follow up’, the investigator or designee must make every effort to regain contact with the subject (where possible, 3 telephone calls and if necessary a certified letter to the subject’s last known mailing address or local equivalent methods). These contact attempts should be documented in the subject’s medical record.
- Should the subject continue to be unreachable, only then will he be considered to have withdrawn from the study with a primary reason of “Lost to Follow-up”.

A subject may withdraw from study treatment at any time at his own request, or may be withdrawn at any time at the discretion of the investigator for safety, behavioural or administrative reasons. If a subject withdraws from the study, he may request destruction of any samples taken, and the investigator must document this in the site study records.

#### **5.5. Subject and Study Completion**

A completed subject is one who has completed all study visits.

The end of the study is defined as the last subject’s last visit.

#### **5.6. Concomitant Medications and Non-Drug Therapies**

##### **5.6.1. Permitted Medications and Non-Drug Therapies**

All medications taken during the study will be recorded in the CRF with indication, dose information, and dates of administration.

##### **5.6.2. Prohibited Medications and Non-Drug Therapies**

Use of prohibited medications, as stated in the exclusion criteria, could potentially affect the value of the data collected. If there is no option other than to administer a prohibited medication, please if possible discuss the procedure with your monitor before administration.

Prohibited medications:

- $5\alpha$ -reductase inhibitors (finasteride or dutasteride),
- anti-cholinergics (e.g. oxybutynin, propantheline, tolterodine, solifenacin, darifenacin, mirabegron) alpha-adrenoreceptor blockers (i.e., indoramin, prazosin, terazosin, tamsulosin, alfuzosin, doxazosin and silodosin), herbal products for urinary symptoms.
- PDE-5 inhibitors for erectile dysfunction
- anabolic steroids

## **6. STUDY ASSESSMENTS AND PROCEDURES**

Protocol waivers or exemptions are not allowed with the exception of immediate safety concerns. Therefore, adherence to the study design requirements, including those specified in the Time and Events Table, are essential and required for study conduct.

This section lists the procedures and parameters of each planned study assessment. The exact timing of each assessment is listed in the Time and Events Table Section [6.1](#)

## 6.1. Time and Events Table

| Procedure   | VISIT 1:
Screening/
Enrolment at GP Clinic | Study Period
(1 week $\pm$ 4 days to 6 weeks) |   |
|---|--|--|---|
|   |  | VISIT 2 (phone call):
GP                      | VISIT 3: Urologist 
(up to 6 weeks after V1) |
| Informed consent  | X  |  |   |
| Inclusion and exclusion criteria  | X  |  |   |
| Demography  | X  |  |   |
| Medical history   | X  |  |   |
| Concomitant medications (all ongoing and within 30 days prior to Visit 1)       | X  |  |   |
| IPSS screening tool   | X  |  |   |
| BPE/BPO screening tool  | X  |  |   |
| PROCEDURES AFTER SUBJECT IS ENROLLED:                        |  |  |   |
| Urine strip test    | X  |  |   |
| Urinalysis (only if urine strip test is positive)                   | X  |  |   |
| PSA blood test    | X  |  |   |
| Results phone call to subject                                       |  | X  |   |
| Digital rectal exam (DRE)   | X  |  | X   |
| Brief physical examination  |  |  | X   |
| Enter prostate-related results in the CRF from non-protocol required procedures |  |  | X   |
| AE/SAE review (related to study procedures and/or participation)                |  | ←=====→  |   |
| Concomitant medication review   |  | ←=====→  |   |

1. Subject is enrolled after meeting eligibility requirements, which includes a positive BPE/BPO screening tool and/or positive IPSS screening tool.
2. Urinalysis sent to local laboratory only if urine strip test is positive.
3. PSA blood test sent to local lab. Local lab results and reference ranges are entered in the CRF.
4. For Visit 2, the GP calls the subject to report yes or no for probable BPH. If the subject has probable BPH, the GP schedules the subject for Visit 3 with the urologist. If the subject does not have probable BPH, then the subject has completed the study.
5. DRE is performed by the urologist. The GP may conduct a DRE at visit 1 however the DRE will be repeated by the urologist to confirm the diagnosis and to rule out an abnormality suggesting prostate cancer..
6. Information collected during visit 3 will be entered into the eCRF by the Principal Investigator.

## 6.2. Screening and Critical Baseline Assessments

The following demographic parameters will be captured: year of birth, and sex.

Medical/medication/family history will be assessed as related to the inclusion/exclusion criteria listed in Section 5.

Patient Reported Outcomes questionnaires should be completed by subjects before any other assessment at a clinic visit, in the order specified.

## 6.3. Safety

### 6.3.1. Adverse Events (AE) and Serious Adverse Events (SAEs)

The definitions of an AE or SAE can be found in Section 11.2.

The investigator and their designees are responsible for detecting, documenting and reporting events that meet the definition of an AE or SAE.

#### 6.3.1.1. Time period and Frequency for collecting AE and SAE information

- Any SAEs assessed as related to study participation (e.g., protocol-mandated procedures, invasive tests, or change in existing therapy) will be recorded from the time a subject consents to participate in the study up to and including any follow-up contact.
- Medical occurrences that begin after obtaining informed consent may be recorded on the Medical History/Current Medical Conditions section of the CRF.
- All SAEs will be recorded and reported to GSK within 24 hours, as indicated in Section 11.2.
- Investigators are not obligated to actively seek AEs or SAEs in former study subjects. However, if the investigator learns of any SAE, including a death, at any time after a subject has been discharged from the study, and he considers the event reasonably related to the study treatment or study participation, the investigator must promptly notify GSK.

NOTE: The method of recording, evaluating and assessing causality of AEs and SAEs plus procedures for completing and transmitting SAE reports to GSK are provided in Section 11.2.

Care will be taken not to introduce bias when detecting AEs and/or SAEs. Open-ended and non-leading verbal questioning of the subject is the preferred method to inquire about AE occurrence. Appropriate questions include:

- “How are you feeling?”
- “Have you had any (other) medical problems since your last visit/contact?”
- “Have you taken any new medicines, other than those provided in this study, since your last visit/contact?”

### **6.3.1.2. Follow-up of AEs and SAEs**

After the initial AE/SAE report, the investigator is required to proactively follow each subject at subsequent visits/contacts. All SAEs (as defined in Section 6.3.1) will be followed until resolution, until the condition stabilizes, until the event is otherwise explained, or until the subject is lost to follow-up (as defined in Section 5.4). Further information on follow-up procedures is given in Section 11.2.

### **6.3.1.3. Regulatory Reporting Requirements for SAEs**

Prompt notification by the investigator to GSK or designee of SAEs related to study treatment or related to a GSK product is essential so that legal obligations and ethical responsibilities towards the safety of subjects are met.

GSK has a legal responsibility to notify both the local regulatory authority and other regulatory agencies about the safety of a product under clinical investigation. GSK will comply with country specific regulatory requirements relating to safety reporting to the regulatory authority, Institutional Review Board (IRB)/Independent Ethics Committee (IEC) and investigators.

Investigator safety reports are prepared for suspected unexpected serious adverse reactions according to local regulatory requirements and GSK policy and are forwarded to investigators as necessary.

An investigator who receives an investigator safety report describing a SAE(s) or other specific safety information (e.g., summary or listing of SAEs) from GSK will file it with the IB and will notify the IRB/IEC, if appropriate according to local requirements.

### **6.3.2. Physical Exams**

- The urologist will perform a brief physical exam.
- Investigators should pay special attention to clinical signs related to previous serious illnesses

### **6.3.3. Clinical Safety Laboratory Assessments**

All protocol required laboratory assessments, must be conducted in accordance with the local laboratory requirements and Protocol Time and Events Schedule.

If additional non-protocol specified laboratory assessments are performed at the institution's local laboratory and result in a change in subject management or are considered clinically significant by the investigator (e.g., SAE or AE or dose modification) the results must be recorded in the CRF.

Refer to the study reference manual (SRM) for appropriate processing and handling of samples to avoid duplicate and/or additional blood draws.

All study-required laboratory assessments will be performed by a local laboratory, apart from:

- Urinalysis strip test

If the urinalysis test strip is positive, then the sample is sent to a local lab for urinalysis.

The results of each test and reference ranges must be entered in the CRF.

PSA chemistry and urinalysis are listed in [Table 1](#).

**Table 1 Protocol Required Safety Laboratory Assessments**

| Laboratory Assessments | Parameters  |
|------------------------|---|
| Routine Urinalysis     | 
 
• Urinalysis strip test
 
• If strip test is positive, send sample to local lab for urinalysis
 
 |
| PSA Chemistry          | 
 
• Submit blood sample to local lab for PSA analysis.
 
  |

### 6.3.4. Urine Sample Collection

A urine strip test will be performed at screening. If the dipstick is positive, a urine sample will be submitted to the local laboratory for urinalysis. Please see the time points listed in Section [6.1 Time and Events Table](#). Results and reference ranges will be entered in the CRF.

## 7. DATA MANAGEMENT

- For this study, subject data will be entered into GSK defined electronic CRFs, transmitted electronically to GSK or designee, and combined with data provided from other sources in a validated data system.
- Management of clinical data will be performed in accordance with applicable GSK standards and data cleaning procedures to ensure the integrity of the data, e.g., removing errors and inconsistencies in the data.
- Adverse events terms and concomitant medications will be coded using MedDRA (Medical Dictionary for Regulatory Activities) and an internal validated medication dictionary, GSKDrug.
- CRFs (including queries and audit trails) will be retained by GSK, and copies will be sent to the investigator to maintain as the investigator copy. Subject initials will not be collected or transmitted to GSK according to GSK policy.

## 8. STATISTICAL CONSIDERATIONS AND DATA ANALYSES

### 8.1. Hypotheses

The primary endpoint is defined as the proportion of men confirmed to have BPH based on full urologist diagnostic testing in men with a positive result on the BPE/BPO screening tool and a probable BPH assessment by GP. Primary endpoint summaries will be descriptively presented in terms of the calculated proportion, described below, and 95% confidence interval on the proportion. Formal hypothesis testing will not be conducted in terms of the primary and secondary endpoint proportions.

### 8.2. Sample Size Considerations

Sufficient general practice centres (approximately 50 subjects per centre) in the various markets will be recruited to administer the BPE/BPO screening tool to 1,500 men using protocol defined criteria presenting to clinic. It is expected that 33% of the 1,500 presenting (or approximately 500) will have a positive result on the BPE/BPO and/or IPSS screening tools and a probable BPH assessment by GP and thus will be assessed by a urologist.

Evaluation of 500 subjects by a urologist will allow estimation of a 95% confidence interval on the primary endpoint proportion with a maximum width of  $\pm 0.044$ . Sample size assumptions are in terms of the binominal distribution with the proportion of urologist confirmed BPH diagnosis most conservatively assigned at 0.50. Using these assumptions, the following provides an overview of other possible sample sizes along with projected 95% confidence interval maximum width.

| Number of Subjects Evaluated by Urologist | Maximum Width of a 95% Confidence Interval |
|---|--|
| 300                                       | $\pm 0.057$                                |
| 500                                       | $\pm 0.044$                                |
| 700                                       | $\pm 0.037$                                |

Sample size re-estimation is not planned.

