## Analysis

- The primary endpoint is defined as the proportion of men that are confirmed to have BPH based on full urologist assessment of diagnostic test results among men with a positive result on the BPE/BPO screening tool and probable BPH diagnosis as assessed by the GP. For this proportion, the numerator is number of subjects diagnosed with BPH by a urologist; denominator is number of subjects with a positive result on the BPE/BPO screening tool and a probable BPH assessment by

the GP and a BPH assessment by the urologist. The 95% confidence interval for this proportion will be presented.

- Sufficient general practice centres (50 consecutive men per centre) in various markets will be recruited to administer the BPE/BPO screening tool to 1,500 men (using protocol defined criteria) presenting to clinic for reasons unrelated to the study. It is expected that 33% of the 1,500 presenting (or approximately 500) will have a positive result on the BPE/BPO screening tool and a probable BPH assessment by GP and thus will be assessed by a urologist.
- Due to the design of the study and types of endpoints incorporated, ‘observed cases’ will be summarized for a subset of subjects in study Parts I and II. There will be no imputations for missing data or for discontinued subjects.
- An interim analysis is not planned for this study.

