### 4. STUDY DESIGN

This non-randomized, interventional study utilizing a questionnaire-based assessment of men in General Practice. Validation of the tool was performed in a previous GlaxoSmithKline (GSK) study (FDC116700: Quick Question Tool Development and Linguistic Validation). Men who sign the informed consent form and meet the eligibility criteria will be enrolled and complete the Part I diagnostic tests at the GP clinic. If the GP determines that the subject has probable BPH (IPSS  $\geq 8$  and/or BPE/BPO questionnaire  $\geq 3$  with a PSA  $\geq 2$  ng/ml), the subject proceeds to Part II and is scheduled for a urologist assessment and diagnostic tests to confirm or refute a BPH diagnosis and to assess risk of progression of BPH.

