#### 4.1. Overall Design

This study is intended to reproduce the circumstances in which the BPH quick tool will be used in General Practice, i.e., in men that may have ‘hidden’ LUTS symptoms. To reproduce these circumstances of opportunistic screening, men will not be invited to attend their GP but **must attend spontaneously with for reasons that are not related to this study**. At this point they will be invited to participate in the study.

GPs participating in the study will recruit men  $\geq 50$  years that present in their clinic for reasons that are not related to this study.

After obtaining informed consent, the GP will initially assess all inclusion and exclusion criteria except for the questionnaire inclusion criterion. If the subject meets those eligibility requirements, the GP administers the BPE/BPO and IPSS screening tools. Subjects who have a positive score on the BPE/BPO screening tool (total score  $\geq 3$ ) and/or the IPSS tool (score  $\geq 8$ ) and meet all other eligibility requirements will be enrolled in Part I of the study. The GP then performs the following diagnostic tests for Part I of the study: urinalysis (sample sent to local lab if the strip test is positive) and Prostate Specific Antigen (PSA) blood test. If the serum PSA result is  $\geq 2$  ng/mL, the GP will make a diagnosis of ‘probable BPH (subjects with symptoms likely to be related to BPH)’ or not. All men with ‘probable BPH’ will proceed to Part II and will be scheduled for Visit 3 with a urologist for confirmation of the GP’s findings plus a brief physical exam and DRE. Additional testing may be performed as per standard of care to assist with a confirmatory diagnosis such as a DRE, however this is not required by the protocol.

The urologist is to:

1) Establish a clinical diagnosis of BPH

AND

2) Estimate whether the patient is at risk of progression of BPH (PSA  $\geq 2.0$  ng/mL and other testing).

For the purposes of this study the diagnosis of the urologist (BPH yes/no) is the operational definition of confirmed BPH. Those men refusing referral to the urologist, but considered by a GP to have BPH (after the tests specified above) will be classified as ‘probable BPH’.

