#### 5.1. Inclusion Criteria

A subject will be eligible for inclusion in this study only if all of the following criteria apply:

|  |
|--|
| AGE  |
| 1. Greater than or equal to 50 ( $\geq 50$ ) years of age at the time of signing the informed consent form.  |
| SEX  |
| 2. Male  |
| INFORMED CONSENT   |
| 3. Capable of giving signed informed consent as described in Section 9.2 which includes compliance with the requirements and restrictions listed in the consent form and in this protocol. |
| OTHER  |
| 4. Present in a General Practice setting for a reason unrelated to this study.   |
| 5. Positive IPSS score ( $\geq 8$ ) and/or positive BPE/BPO screening tool score ( $\geq 3$ ).   |

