### **8.4.2. Primary Analyses**

The primary endpoint is defined as the proportion of men confirmed to have BPH based on full urologist diagnostic testing among men with a positive result on the BPE/BPO screening tool (score  $\geq 3$ ) and serum PSA  $\geq 2$  ng/mL. Primary endpoint summaries will be descriptively presented in terms of the calculated proportion, described below, and 95% confidence interval on the proportion. Formal hypothesis testing will not be conducted.

| Tool        | Proportion  | Numerator  | Denominator  |
|-------------|---|--|--|
| BPE/
BPO | BPH Diagnosis by Urologist based upon BPE/BPO screening tool (score $\geq 3$ ) and serum PSA $\geq 2$ ng/mL | Number of subjects diagnosed with BPH based on full urologist diagnostic testing | Number of subjects with a positive result on the BPE/BPO screening tool (score $\geq 3$ ) and serum PSA $\geq 2$ ng/mL and a BPH assessment by urologist |

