**8.1.2. Planned Secondary Efficacy Statistical Analyses**

Primary Statistical Analyses			
Endpoint(s)			
Secondary endpoints and other measures of interest are defined in terms of proportions for each: probable BPH diagnosis by GP, BPH diagnosis by Urologist, and BPH progression risk by Urologist along with use of 1) BPE/BPO screening tool and 2) IPSS screening tool. The 95% confidence intervals (calculated using the exact (Clopper-Pearson) method) for these proportions will be presented.			
Secondary Endpoints: Proportions only in terms of the BPE/BPO tool			
Tool	Proportion	Numerator	Denominator
BPE/BPO	BPH Progression Risk by Urologist based upon BPE/BPO screening tool (score $\geq 3$ ) and serum PSA $\geq 2$ ng/mL	Number of subjects diagnosed with BPH progression risk by Urologist	Number of subjects with a positive result on the BPE/BPO screening tool (score $\geq 3$ ) and serum PSA $\geq 2$ ng/mL and a BPH progression risk assessment by Urologist
BPE/BPO	Probable BPH Diagnosis by GP based upon BPE/BPO screening tool (score $\geq 3$ )	Number of subjects diagnosed with 'probable BPH' by GP	Number of subjects with a positive result on the BPE/BPO screening tool (score $\geq 3$ ) and a BPH assessment by GP

Primary Statistical Analyses			
Secondary Endpoints: Proportions only in terms of the IPSS screening tool			
Tool	Proportion	Numerator	Denominator
IPSS	BPH Diagnosis by Urologist based upon IPSS (score $\geq 8$ ) and serum PSA $\geq 2$ ng/mL	Number of subjects diagnosed with BPH based upon BPH assessment by Urologist.	Number of subjects with a positive result on the IPSS (score $\geq 8$ ) and serum PSA $\geq 2$ ng/mL and a BPH assessment by Urologist
IPSS	BPH Progression Risk by Urologist based upon IPSS (score $\geq 8$ ) and serum PSA $\geq 2$ ng/mL	Number of subjects diagnosed with BPH progression risk by Urologist	Number of subjects with a positive result on the IPSS (score $\geq 8$ ) and serum PSA $\geq 2$ ng/mL and a BPH progression risk assessment by Urologist
IPSS	Probable BPH Diagnosis by GP based upon IPSS (score $\geq 8$ )	Number of subjects diagnosed with 'probable BPH' by GP	Number of subjects with a positive result on the IPSS (score $\geq 8$ ) and a BPH assessment by GP

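### The ±0.044 maximum for the primary endpoint rests on 500 men positive on either tool, but the primary denominator admits only BPE/BPO-positive men

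*Protocol*

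**What the plan says.** Protocol 8.2 expects 33% of 1,500 men, about 500, to show "a positive result on the BPE/BPO and/or IPSS screening tools and a probable BPH assessment by GP and thus will be assessed", meaning at the urologist visit. It then says: "Evaluation of 500 subjects by a urologist will allow estimation of a 95% confidence interval on the primary endpoint proportion with a maximum width". The figure it gives is ±0.044, from the binomial distribution with the proportion set at 0.50. Its table gives ±0.057 for 300 men, ±0.044 for 500 and ±0.037 for 700, indexed by the number evaluated by a urologist. Sample size re-estimation is not planned.

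The Analysis part of the protocol synopsis uses the same 33% and 500 but describes a narrower group: these men "will have a positive result on the BPE/BPO screening tool and a probable BPH assessment by GP and thus will be assessed", again at the urologist visit. The IPSS is not mentioned there.

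The primary denominator in Protocol 8.4.2 is the "Number of subjects with a positive result on the BPE/BPO screening tool" (score ≥3) who also have serum PSA ≥2 ng/mL and a BPH assessment by the urologist. SAP 7.1.2 repeats it.

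The route to the urologist is wider. Inclusion criterion 5 (Protocol 5.1) accepts IPSS ≥8 "and/or positive BPE/BPO screening tool score" of ≥3. Protocol 4 describes probable BPH as IPSS ≥8 "and/or BPE/BPO questionnaire" ≥3, with PSA ≥2 ng/mL. Protocol 4.1 says that all men with probable BPH "will proceed to Part II and will be scheduled for Visit 3 with a urologist for confirmation".

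**The concern.** A man with IPSS ≥8, BPE/BPO <3 and PSA ≥2 ng/mL can be enrolled, called probable BPH by the GP and seen by the urologist. He is one of the 500 in section 8.2, yet the primary denominator excludes him. The n behind ±0.044 is therefore an upper limit on the primary denominator that section 8.2 itself envisages.

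The synopsis and section 8.2 can both be right only if almost nobody is referred on the IPSS alone. No section says so. The plan reports results separately for each tool, for both and for either, and estimates kappa between the tools, so it treats their agreement as unknown.

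No hypothesis is tested on the primary proportion. This half-width is the only justification given for the sample size.

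**Working it through.** **Inputs.** 95% confidence, z = 1.96; p = 0.50; n = 500; table rows 300, 500 and 700 (all Protocol 8.2). The denominator is from Protocol 8.4.2 and SAP 7.1.2. The share of referred men positive on the IPSS alone is not given, so it is varied below as an assumption.

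**1. Reproduce the plan's figures.** The Wald half-width at p = 0.50 is 1.96 × √(0.25/n) = 0.98/√n.

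- n = 300: 0.0566, printed 0.057
- n = 500: 0.0438, printed 0.044
- n = 700: 0.0370, printed 0.037

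All three agree. The plan calls these widths; they are half-widths.

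**2. How far can n fall before the printed 0.044 fails?** To round to 0.044 the half-width must be below 0.0445, so n ≥ (0.98/0.0445)² = 484.99, i.e. 485. At n = 484 it is 0.04454, which prints as 0.045. The IPSS-only share at n = 485 is 1 − 485/500 = 3.0%. With no rounding allowance, n ≥ (0.98/0.044)² = 496.1, i.e. 497.

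**3. Half-width for the primary denominator, n = 500 × (1 − assumed IPSS-only share), at p = 0.50.** The Clopper-Pearson column is half the exact interval's length at x = n/2 or the nearest counts.

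| IPSS-only share (assumed) | n | Wald | Clopper-Pearson |
|---|---|---|---|
| 0% | 500 | 0.0438 | 0.0447 |
| 5% | 475 | 0.0450 | 0.0459 |
| 10% | 450 | 0.0462 | 0.0472 |
| 20% | 400 | 0.0490 | 0.0501 |
| 30% | 350 | 0.0524 | 0.0536 |
| 40% | 300 | 0.0566 | 0.0580 |

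The exact column is shown because SAP 8.1.2 has the secondary intervals "calculated using the exact (Clopper-Pearson) method", while SAP 7.1.2 names no method for the primary. Under the exact method even n = 500 prints as 0.045, and about 505 men are needed to print 0.044.

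**4. When would the realised interval still be within ±0.044?** Setting 1.96 × √(p(1 − p)/n) = 0.044 gives p(1 − p) = n × (0.044/1.96)².

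- n = 450: p(1 − p) = 0.2268, so p ≥ 0.652 or p ≤ 0.348
- n = 400: p(1 − p) = 0.2016, so p ≥ 0.720 or p ≤ 0.280

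With the rounding allowance of step 2 (0.0445), the upper limits become about 0.634 and 0.709.

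**The case against.** The best counter-argument is that no shortfall has been shown. On the synopsis wording all 500 men are BPE/BPO-positive and ±0.044 stands. The IPSS-only share appears nowhere, so every loss figure is an assumption. The table already prints the n = 300 row, which matches the 40% case, and Protocol 8.3.1 warns that evaluable numbers will shrink by endpoint. The 3% threshold turns on the third decimal of a plan that says approximately 500; 33% of 1,500 is 495, which gives 0.98/√495 = 0.0440. No decision depends on the width, and the unnamed interval method is a separate matter.

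Much of this stands. There is no formula error, the loss is modest if few men are IPSS-only, and 3% marks a rounding boundary with no clinical meaning. The difference of about 0.0009 between methods at n = 500 is minor and the conclusion does not need it.

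It does not remove the mismatch. Section 8.2, the operative sample size section, states the wider group and then attaches its n to the primary endpoint. The synopsis contradicts that section without correcting it. Neither Protocol 8.3.1 nor the n = 300 row tells the reader that the primary denominator may be smaller than the number evaluated by a urologist.

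**Conclusion.** The point holds. The ±0.044 is right for 500 men at p = 0.50, but section 8.2 counts men whom the primary denominator excludes, so that maximum is not assured. It fails at an IPSS-only share above about 3%; assumed shares of 10%, 20%, 30% and 40% give Wald maxima of 0.046, 0.049, 0.052 and 0.057. These rest on p = 0.50, on exactly 500 men evaluated, and on shares the documents do not supply. The realised interval could be narrower if the true proportion is well away from 0.50.

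The consequence is limited to planning. The estimate and its reported interval will use the actual denominator and are not biased; the stated worst-case precision may be too favourable.

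**What to change.** - Use one definition of the 33% and 500 in the synopsis and in Protocol 8.2.
- In 8.2, state the expected number of men in the primary denominator (BPE/BPO ≥3, PSA ≥2 ng/mL, assessed by a urologist) and the IPSS-only share assumed to reach it. If no estimate exists, give a range.
- Restate the primary endpoint's maximum half-width for that number under the interval method to be used, and name the method in SAP 7.1.2.
- Relabel the table's first column as the number of subjects in the primary denominator. Possible rows (Wald / Clopper-Pearson): 300, 0.057 / 0.058; 350, 0.052 / 0.054; 400, 0.049 / 0.050; 450, 0.046 / 0.047; 500, 0.044 / 0.045.

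The cost is one phrase aligned, a sentence or two added and one column relabelled, with a slightly less favourable stated precision. The correction itself requires no extra enrolment. If the sponsor prefers to keep 500 men in the primary denominator, it would need 500/0.9 = 556 referrals (about 1,667 screened at the plan's one-third yield) at a 10% IPSS-only share, or 500/0.8 = 625 (1,875 screened) at 20%.
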